#### 2. Project outline

#### 2. Main study design

This will be a two-*arm*, active comparator, *double-blind*, *randomized controlled*, betweensubjects, design in up to *60 completing* patients meeting DSM-IV criteria for *major depression* of a moderate to severe degree (17+ on the 21-item Hamilton Depression Rating Scale, HAM-D). The patients will be randomly allocated to two groups. Groups will receive either: 1) two on-site dosing sessions with 25mg p.o. psilocybin, 3 weeks apart, the first dosing session being followed by 6 weeks of daily inert placebo ingestion, 2) two dosing sessions with 1mg psilocybin (to our knowledge, sub-psychoactive), 3 weeks apart, the first dosing session being followed by 6 weeks of daily escitalopram (10 mg for the first 3 weeks then increasing to 20 mg for 3 weeks, in line with prescribing guidelines [79] and similar to previous literature [98]). See Figure 1 for details.

Condition one is the main experimental condition and condition 2 is a control condition. Condition 2 involves 6-weeks of treatment with a gold-standard antidepressant, escitalopram, adding an important comparative efficacy component to this trial. Both groups will receive equal preparation and follow-up before and after the dosing session. The blind is broken after 6 weeks, after which normal treatment ensues.

**Figure 1. Basic design.** Active components are highlighted in red. Please note, the psilocybin 'dosing sessions' are variously called 'dosing days' in what follows

#### 2.1. Dose

## 2.1.1. Psilocybin

Patients in condition 1 will receive two doses of 25mg, 3 weeks apart from each other. In our recent open label feasibility study, this dose was well tolerated by all of the patients; no serious or unexpected adverse events occurred, and the mean patient rating of intensity of drug effects

was 7.5 (+2.5) out of 10, which was what we had planned to achieve. Based on these observations we feel confident that this dose maximises the potential for therapeutic benefit, whilst minimising the risk of acute adverse events. This view has been further supported by our conversations with other researchers working with psilocybin, such as those at Johns Hopkins University.

Regarding the control group, 1mg psilocybin has been chosen because evidence indicates it is pharmacologically 'inert' and yet capable of serving as an effective placebo [4], producing effects via expectancy alone, to a similar degree as a non-active placebo. Positive expectation is the major psychological factor underlying the 'placebo' effect, so the merit of using psilocybin in both conditions is that study staff and patients can be briefed to expect psilocybin in all conditions. Patients and therapy staff will be encouraged to expect and prepare for up to 25mg of psilocybin; thus, standardizing preparation and expectations prior to the dosing session.

## 2.1.2. Escitalopram

Escitalopram is a highly selective serotonin reuptake inhibitor (SSRI) that was licensed in the US in 2002 as an approved treatment for major depressive disorder. It has since been prescribed to millions of people worldwide, becoming a gold-standard medication for depression. Meta-analyses have indicated that escitalopram is one of the best performing SSRIs in terms of tolerability and efficacy [77] and it is one of the most selective SSRIs [78].

Patients in condition 2 who receive an inactive dose of psilocybin (1mg) during the first dosing day, will subsequently receive 6 weeks of daily escitalopram. For the first 3 weeks they will receive 10mg-daily (1 capsule per day). After 3 weeks they will have a second 1mg psilocybin dosing day (without interrupting the daily escitalopram dosing schedule). After this, they will subsequently take 20mg of escitalopram daily (2 capsules per day) for three further weeks. The dose of 20mg is the recommended maximum dose for this commonly prescribed primary treatment for depression, and thus we would expect the patient's symptoms of depression to decrease. It would be expected that patients starting a course of SSRIs would report some improvements in depressive symptoms after even this relatively brief treatment period of 6 weeks [80, 81].

The dose of escitalopram can be lowered to 10mg from 20mg if patients appear not to be tolerating 20mg and ask to lower the dose or withdraw from the trial. This would be simple to implement as we would just instruct patients to take 1 capsule daily instead of 2. If, when the blind is broken at the 6 week endpoint, it transpires that the patient was actually in condition 1 and not in fact in the escitalopram condition, this would be logged.

We will be monitoring patients' response to escitalopram via weekly self-report measures, and measures of side effects. FDA guidelines report the following possible side-effects with escitalopram: headaches, dizziness, nausea, insomnia, dry mouth, impotence, decreased appetite, weight gain, vomiting, vivid dreams and a tingling sensation in arms, hands, feet and legs [79]. Insomnia and diarrhea are the most common side-effects, affecting 15% of individuals at 20mg [79].

When the blind is broken at the end of the 6-week course, the study psychiatrist will conduct individual consultations with patients in condition 2 to discuss whether they would like to continue with escitalopram or return to treatment as usual after controlled withdrawal. The patient's GP/psychiatrist will be included in treatment planning/medication withdrawal.

Patients in condition 1 will receive daily placebo (inert) instead of escitalopram over the same 6-week period following the psilocybin dose (fig. 1). The study psychiatrist will also advise patients in condition 1 about treatment options after the trial.

## 2.2 Data Collection

#### 2.2.1 Outcome Measures

The primary efficacy outcome measure will be the Quick Inventory of Depressive Symptoms (QIDS) and changes from baseline to 6-weeks after the psilocybin dosing session. The QIDS measures internal states including most of the diagnostic criteria for depression and is sensitive to treatment effects [6].

The 16-item QIDS will be collected weekly from the moment of enrolment up to 6 weeks after dosing [12]. It will also be done one day before dosing and one day after dosing (using a version of this scale tailored to daily use [82]). After 6 weeks, measures will be collected monthly, up to 6 months post-dosing. Secondary outcomes include (but are not limited to): additional patient (BDI) and clinician (HAM-D) depression rating scales, well-being (WEMWBS), anxiety (STAI), optimism (LOT-R), personality (BIG-5) and others, plus all imaging outcomes (e.g. anatomical measures, including: morphometry, cortical thickness and tractography; functional measures, including: CBF, BOLD RSFC, signal variance and entropy/complexity, and activations to emotional faces). After the 6-week post dosing day primary end-point, subsequent follow-up will be done remotely with the exception of a structured interview at 1 month and 6 months.

#### 2.2.2 Automated prompts for data completion and participant duties

The Psychedelic Survey platform (psychedelicsurvey.com) is an external software that was created for a recent cohort study conducted by our group (results still unpublished). It was

used to automate reminder emails to a large number of participants over the course of a few months. These emails linked participants to questionnaires contained within the separate Survey Gizmo platform, where we stored our data. This was found to be an efficient way to optimise collection and safe storage of questionnaire data, so this procedure will be repeated for this trial. Using these platforms is an effort to minimise the chance of human error and ensure the large volumes of data are collected correctly over the course of the trial.

For this study, the Psychedelic Survey platform will be programmed to send automatic patient reminders, including:

- 1. Reminding patients to take escitalopram/placebo every morning, promoting compliance
- 2. Reminding patients to complete their weekly/monthly QIDS questionnaires. This reminder will have a link to the Survey Gizmo platform, where patients will have an individual login and can complete the questionnaires online.
- 3. Reminding patients of any extra questionnaires to be completed
- 4. Reminding patients of onsite meetings

Reminders will be sent by both text message and email at specific times programmed by the study researchers. A limited number of study staff will be able to login to the Psychedelic Survey to amend or update patient reminders.

The Psychedelic Survey platform will only have access to patient email addresses and phone numbers, no other personal/medical data. This data is considered personal but not sensitive, so this project will be in accordance with Schedules I and II of the Data Protection Act [94]. Patient consent will be obtained and will not be necessary for inclusion in the study (see patient consent form). In accordance with the Data Protection Act [94], this personal data will only be used for the purposes of sending reminders and will be deleted after the study is over. More information is available on the Psychedelic Survey's Privacy Policy (attached as an appendix).

Questionnaire data will be stored within the Survey Gizmo platform and not the Psychedelic Survey platform. This has been done in previous studies by our group [95 and unpublished cohort study which launched the Psychedelic Survey platform]. Only study staff will have access to this information and both staff and patients will have individual logins for the website. The Research Data Manager for this study ([name]) will keep track of incoming data and patient reminders via these two platforms throughout the clinical trial period.

#### 2.3. Recruitment

## 2.3.1. Key entry criteria

Key inclusion criteria:

- 1. Major depressive disorder (DSM-IV)
- 2. Depression of moderate to severe degree (17+ on the 21-item HAM-D).
- 2. No MRI contraindications
- 3. No SSRI contraindications
- 4. Has a GP or other mental healthcare professional who can confirm diagnosis
- 5. 18-80 years of age
- 6. Males and females
- 7. Sufficiently competent with English language

Key exclusion criteria:

- 1. Current or previously diagnosed psychotic disorder
- 2. Immediate family member with a diagnosed psychotic disorder
- 3. Medically significant condition rendering unsuitability for the study (e.g., diabetes, epilepsy,

severe cardiovascular disease, hepatic or renal failure e.g. CLRC < 30 ml/min etc.)

- 4. History of serious suicide attempts requiring hospitalisation.
- 5. Significant history of mania (determined by study psychiatrist and medical records)
- 6. Psychiatric condition judged to be incompatible with establishment of rapport with therapy team and/or safe exposure to psilocybin, e.g. borderline personality disorder
- 7. Blood or needle phobia

8. Positive pregnancy test at screening or during the study, women who are planning a pregnancy and/or women who are nursing/breastfeeding.

9. Participants who do not agree to use an acceptable contraceptive method throughout their participation in study (see section 7.2.1).

10. Current drug or alcohol dependence

- 11. No email access
- 12. Use of contraindicated medication

13. Patients presenting with abnormal QT interval prolongation at screening or with a history of this (QTc at screening above 440ms for men and above 470ms for women)

## 2.3.2. Drug interactions [86]

## - Specifically for escitalopram:

MAOIs (escitalopram should not be started until 2 weeks after stopping MAOIs, and MAOIs can not be started until one week after stopping escitalopram), TCIs, Amiodarone, Artemether with Lumefantine, Artenimol with Piperaquine, Chloroquine, Cimetidine, Disopyramide, Dronedarone, Erythromycin, Haloperidol, Metoprolol, Mizolastine,

Moxifloxacin, Pentamidine Isetionate, Phenothiazines, Pimozide, Quinine, Sotalol, Sumatriptan. Caution with Omeprazole (increases plasma concentration of escitalopram), and Metoprolol (escitalopram increases plasma concentration of metoprolol).

## - Additional for SSRIs in general – and thus also for escitalopram:

5HT3-receptor antagonists, Antiepileptics, Aspirin (should be avoided), Coumarins, Cyproheptadine, Dabigatran, Dapoxetine, Duloxetine, Fentanyl, Lithium, Methylphenidate, Methylthioninium, Metoclopramide, NSAIDs (should be avoided), Naratriptan, Pimozide, Rasagiline, Ritonavir, St John's Wort, Tramadol, Vortioxetine.

Patients currently receiving any of these medications will either be asked to discontinue them in an appropriate way (where indicated), or they may be excluded from the trial.

## Contraindicated medications for escitalopram include [86, 87]:

- MAOIs
- Procarbazine

- NSAIDs (including) Aspirin should be avoided during the course of the trial, as they may cause GI bleeding [86].

- Medicines that prolong QT interval, including [99]:

- Cardiac medications: Class 1a (Quinidine, Procainamide, Disopromide) and Class III (Dofetilide, Ibutilide, Sotalol) Antiarrythmic drugs
- Antihistamines (Terfenadine, Astemizole)
- Antipsychotics: Haloperidol, Droperidol, Thioridazine, Sertindole\*, Ziprasidone, Risperidone, Zimeldine, Chlorpromazine
- Antidepressants: Citalopram, Amitriptyline, Desipramine, Imipramine, Maprotiline, Doxepin, Fluoxetin
- Antibiotics: Quinolone (Sparfloxacin, Levofloxacin, moxifloxacin, grepafloxacin) and Macrolide (Erythromycin, Clarithromycin)
- Antimalarials (Quinine, halofantrine)
- Antiprotozoal (Pentamidine)
- Antifungal (Azole group)
- Antimotility agents (Cisapride)
- Methadone

Antipsychotic medications and mood stabilisers may attenuate the effects of psilocybin and so are also contraindicated for this reason. However, such medications are usually only prescribed for manic and/or psychotic illness, and patients presenting with such histories would be excluded from the study. Details regarding discontinuation of antidepressant medications can be found below (2.4.1).

#### 2.3.3. Recruitment strategy

To minimise/address pre-study biases, recruitment will predominantly be via referrals (we have good links with Clinical Research Networks (CRNs), Improving Access to Psychological Therapies (IAPT), local clinics and clinicians) and Clinical Record Interactive Search systems (CRIS Health Ltd). A Facebook page has also been created for the trial in order to aid recruitment, which will be managed by the team: https://www.facebook.com/Psilodep-RCT-334207224132116/. Prior attitudes to treatments will be collected at baseline and entered into regression analyses. Patients will be randomly allocated to one of the two conditions after eligibility is confirmed post screening. We will endeavour to recruit patients who are currently unmedicated for their depression. Where patients are medicated, withdrawal from antidepressants would be required prior to participation and this process would be done with adequate washout and appropriate titration and carefully monitored in collaboration with the patient and their primary care giver

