#### 2.4.1 Managing risks related to withdrawal from antidepressants

PSILODEP RCT – Study Protocol, Version 7, 11/07/2019

Serotonergic antidepressants are known to attenuate the acute psychological effects of psychedelics [8] and thus, we feel it is necessary that patients withdraw from these medications in order to experience the full effects of the 25mg dose of psilocybin. This washout component of the design is consistent with our recent pilot study, as this was done safely and effectively in that trial. Withdrawal symptoms and a worsening of depressive symptoms can occur with antidepressant-withdrawal [9]; thus, we will incorporate a number of contingency measures to reduce associated risks, namely:

1) Patients will be free to leave the study at any point and return to their treatment as usual if they, their mental-health care-giver or the study team feel this is the right course of action.

2) The study blind will be broken at 6-weeks after the initial dosing session (fig 1), enabling patients to return to pre-study treatment/s if they so choose.

3) Study clinicians will offer telephone contact to patients during the withdrawal period, if this is required.

It is important to note that since recruitment to this trial is not restricted to patients with treatment-resistant depression, potential volunteers may well be unmedicated at the time of study entry. Thus, we can anticipate that challenges relating to withdrawal from medication will be less than in our previous open-label trial in treatment-resistant depression. Even so, antidepressant medication withdrawal was managed safely and effectively in that trial and we foresee that the same will be true in this trial.

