of medications, we will discuss with the patient and their GP or mental health caregiver whether the patient should withdraw from the trial so that previous medications can be resumed or new ones given. There will be ~7 weeks from the first (post-screening) study visit (**visit 2, scan 1**) to the primary end point/blind broken (**visit 7**), after which patients may return to their normal treatments if they so wish.

Patients will be required to make **7 visits** (see fig. 2). Patients will be assessed for up to six months after the initial dosing session; however, the study blind will be broken 6 weeks after the dosing session. Treatment as normal can then take place after the study blind has been broken.

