## 2.6. Visits

## Visit 1: Screening

Screenings typically take up to **4.5 hours** and include a physical examination by the study doctor, an ECG, and a period of MRI scanner acclimatisation, i.e. the patient will be invited to spend a period lying in an MRI scanner to assess whether they can tolerate the environment/conditions. Consent to enter the study will be sought from each participant after a full explanation has been given, the study information sheet has been issued and time allowed for consideration. Signed informed consent will be obtained for each patient.

We will know whether or not the patient is eligible for the trial ~3-days post screening (depending on receipt of relevant confirmation of diagnosis from the patient's GP or psychiatrist). As soon as eligibility is confirmed, the patient will be randomly allocated to one of the two study conditions.

If eligible, and if the patient wishes to participate in the trial, as soon as study entry is confirmed, a patient taking antidepressant medication will be required to begin coming off this medication, in a gradual, tapered fashion. We will ask that they inform their primary care giver of their decision to do this and we will manage medication withdrawal with their awareness. Medication withdrawal is typically done via gradual titration (e.g. halving of dose in first week) and the study psychiatrist will oversee this process in correspondence with the patient's GP and/or psychiatrist.

As soon as entry into the trial is confirmed, patients will be asked to complete the weekly QIDS-16 [12].. Patients will complete this up until the 6-week post dosing day, when the blind is broken. Use of the QIDS-16 [12] will enable us to track patient's mental health for the duration of the trial, facilitating patient monitoring and safety, while providing potentially useful data on weekly mood cycling pre versus post treatment [42].

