## 12. Randomisation

Patients will be randomly allocated to one of the 2 conditions using a random sequence generator such as can be found online:

(https://www.random.org/sequences/?min=1&max=66&col=3&format=html&rnd=new). The sequence can be initiated and managed by the dispensing pharmacist and schedule 1 license holder (Invicro, previously Imanova). Blinding and labelling will be done in collaboration with the manufacturing pharmacy (e.g. GSTT, Juniper and Fisher pharmaceuticals). An example of a random sequence for 2 conditions is provided below:

Condition 1	Condition 2
2	1
3	4
5	6
8	7
10	9
12	11
13	14
15	16
18	17
19	20
22	21
24	23
25	26
27	28
30	29
32	31
34	33
35	36
38	37
40	39
41	42
43	44
46	45
48	47
50	49
51	52
54	53
56	55
57	58
60	59

**Table 1.** Example of a random sequence by which patients recruited to the trial enter the relevant conditions. This sequence is held by the dispensing pharmacy (at Invicro) who do not disclose the randomisation to the study team until situations where the blind is broken.

Patient numbers will be independently monitored by InForm, the data system used by Imperial's in house Clinical Trials Unit (Imp-CTU). Versions of objective tests will be counterbalanced using the same randomisation code (e.g. to ensure a 50:50 split, versions A and B will alternate, with version A provided first). Invicro will also direct the study team as to what version of tests will be used and they will also keep their own detailed log of which patients enter which condition. The Imp-CTU system uses InForm ITM (Integrated Trial Management) System, a web-based data entry system which builds an Oracle database for each individual clinical trial.

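### Allocation is not stratified by antidepressant withdrawal, leaving an avoidable risk of chance imbalance at 30 per arm; the contrast itself stays unbiased

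*Protocol*

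**What the plan says.** **Who enters.** Protocol section 2.3.3 states a preference, "We will endeavour to recruit patients who are currently unmedicated for their depression", and then admits the others: "Where patients are medicated, withdrawal from antidepressants would be required prior to participation". No cap or quota is given. Section 2.4.1 expects fewer withdrawal problems than in the treatment-resistant pilot, but gives no share.

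**How they are allocated.** Section 2.6 (Visit 1) says: "As soon as eligibility is confirmed, the patient will be randomly allocated to one of the two study conditions". Section 12 adds: "Patients will be randomly allocated to one of the 2 conditions using a random sequence generator such as can be found online". The example list there splits each consecutive pair of patients between the arms, so it controls arm size. No stratification factor is named.

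**Why status may matter.** Section 2.4.1 says: "Withdrawal symptoms and a worsening of depressive symptoms can occur with antidepressant-withdrawal". Section 4.1.2 takes the QIDS baseline at screening, whereas tapering begins only after study entry is confirmed (section 2.6, Visit 1). From the morning after session 1, condition 2 takes daily escitalopram (sections 2.1.2 and 2.6, Visit 3). For the other arm: "Patients in condition 1 will receive daily placebo (inert) instead of escitalopram over the same 6-week period".

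**Analysis.** Section 10 says the study is powered for a t-test between conditions on the QIDS. Section 2.3.3 foresees regression analyses that include prior attitudes to treatment.

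**The concern.** The change score for a withdrawn patient runs from a medicated screening visit, through taper and washout, to week 6. For an unmedicated patient it contains no taper. Any worsening from withdrawal that persists therefore enters the primary efficacy measure directly. After washout, withdrawn patients in condition 2 go back on an antidepressant and those in condition 1 do not.

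A baseline factor with a plausible effect on the outcome, known before allocation, is thus left to chance in a trial of 60. An uneven split would add noise to the QIDS contrast, and possibly to the amygdala contrast, whose baseline scan follows washout (section 4.1.1). It would also leave an awkward table of baseline characteristics to explain when the result is read.

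**Working it through.** **Inputs from the protocol (section 4.2.1).** Pilot reduction 9.2, SD 5.6; control reduction printed as 4.7; 80% power, p < 0.05; 20 per condition required, 30 per condition planned.

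**Assumptions, because the protocol gives no figure.** Share withdrawn m = 20-50%. Gap g in mean QIDS change between withdrawn and unmedicated patients = 3-5 points. SD 5.6 holds within each group.

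**1. The plan's own figure.** n per arm = 2 × SD² × (z_α + z_β)² / d², with d = 9.2 − 4.7 = 4.5.
- One-sided 5%: 2 × 31.36 × 6.18 / 20.25 = 19.1, so 20, which matches.
- Two-sided 5%: 2 × 31.36 × 7.85 / 20.25 = 24.3, so 25.

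Sidedness is a separate matter. What is needed here is the standard error at 30 per arm: 5.6 × √(2/30) = 1.45 points.

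**2. Chance imbalance of at least 6 patients between arms of 30.**

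| Share withdrawn | Independent binomial counts | Total withdrawn fixed (hypergeometric) |
|---|---|---|
| 20% | 7.5% | 10.4% |
| 30% | 12.0% | 15.8% |
| 40% | 14.7% | 18.7% |
| 50% | 15.5% | 19.6% |

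The binomial column also applies to the pairwise example list if status is independent from patient to patient.

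**3. Effect of an imbalance of 6.** Shift = g × 6/30. For g = 3 it is 0.6 points, and 0.6/1.45 = 0.4 SE. For g = 5 it is 1.0 point, and 1.0/1.45 = 0.7 SE.

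**4. Share of variance.** m(1−m)g² / [m(1−m)g² + 5.6²].
- Lowest, m = 0.2 and g = 3: 1.44 / 32.80 = 4.4%.
- Highest, m = 0.5 and g = 5: 6.25 / 37.61 = 16.6%.

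**5. Dependence on the mix.** Suppose the treatment difference is 4.6 points (half of 9.2, used only for scale) in unmedicated patients and 4.6 + h in withdrawn patients. The pooled difference is 4.6 + h × m. Power is for a two-sided 5% t-test at 30 per arm.

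| Share withdrawn | h = −3: pooled, power | h = +3: pooled, power |
|---|---|---|
| 20% | 4.0, 78% | 5.2, 94% |
| 40% | 3.4, 64% | 5.8, 98% |
| 60% | 2.8, 48% | 6.4, 99% |

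With no interaction, power is 88%. The protocol gives neither the sign nor the size of h. Stratified allocation leaves every entry in this table unchanged, because it balances the arms and does not set m.

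**6. Precision of a comparison between strata.** SE of interaction = 5.6 × √(2/n₁ + 2/n₂), with n₁ + n₂ = 30 per arm. At 20% (6 and 24) it is 3.6; at 30% it is 3.2; at 50% (15 and 15) it is 2.9. The 95% half-width is about 6-7 points, wider than the 4.6-point difference itself.

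**The case against.** Randomisation makes the pooled contrast unbiased, and the test's error rate already allows for chance imbalance. Most of the precision gain comes from adjusting for the factor, which works without stratified allocation and may be in a statistical analysis plan that is not shown. All of this stands. What remains is that section 12 fixes the allocation method, and the factor could be balanced there at almost no cost.

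Two stronger readings are tempting.

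- **That relief of withdrawal in condition 2 masks a benefit of psilocybin.** The documents give no direction for this. HAM-D of 17 or more is scored at screening, before tapering, so medicated entrants were at least moderately depressed while on treatment. They might respond less to another antidepressant, which would widen the contrast. Section 2.5 also requires washout (4 weeks for fluoxetine, 2 weeks otherwise) before the first study day. Where symptoms increase markedly, it provides for a discussion of "whether the patient should withdraw from the trial so that previous medications can be resumed or new ones given". That passage concerns leaving the trial. It does not make medication within the trial the answer to withdrawal. Departures by this route could also make the real gap smaller than assumed here.
- **That stratifying would settle what the pooled estimate means.** It would not: the mix would still be whatever is enrolled, and the stratum estimates are too imprecise to resolve the question.

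**Conclusion.** The point holds as one of efficiency and chance imbalance. Patients withdrawn for the trial and unmedicated patients share one unstratified sequence, and the protocol's own text makes this status a plausible influence on the QIDS change score. At 30 per arm, an imbalance of at least 6 patients has a probability of about 7-16% (10-20% with the total withdrawn fixed). It would shift the contrast by 0.6-1.0 points, or 0.4-0.7 SE. The factor would account for about 4-17% of variance.

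These sizes rest on an assumed 20-50% withdrawn and an assumed gap of 3-5 points. A smaller gap reduces the shift in proportion. No figure can be given for the amygdala outcome. If the treatment difference varies by status, in either direction, the pooled estimate also depends on the enrolled mix, and stratification does not alter that. The trial is not biased by the omission, and the protocol does not contradict itself on this point.

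**What to change.** - **Section 12:** the pharmacist holds two blocked allocation lists, one for patients on an antidepressant at screening and withdrawn for the trial, and one for patients not on an antidepressant at screening. The study team sends the status with the patient identifier when allocation is requested.
- **Analysis:** include this stratum as a factor in the week-6 QIDS and amygdala analyses, if the statistical analysis plan does not already do so.
- **Reporting:** give the number of patients per stratum and arm, and the stratum-specific QIDS contrasts with confidence intervals, labelled as descriptive only.

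**Cost:** one extra field for the pharmacist and a few lines of text, with no additional patients or visits and no change to treatment. The drawback is that the stratum estimates will be imprecise (interaction SE about 2.9-3.6 points), and the report should say so to discourage over-reading.
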